2.3 Sample size

Because we will target patients at higher risk of readmission, we hypothesize that the intervention could reduce the relative risk of readmission by 25%, i.e. more than the 18% reduction found in a recent meta-analysis where patients were mostly not at high risk for readmission. Based on previous findings, the expected 30-day readmission and death rate for patients at intermediate or high risk according to the simplified HOSPITAL score is around 27%. Allowing for 10% loss to follow-up, we determine that we will need 1,380 patients for the study to have 80% power, i.e. 690 in each arm.

The intervention phase (randomized controlled trial) will be restricted to the eligible patients who are at intermediate to high risk of 30-day readmission according to the simplified HOSPITAL score, i.e. $\geq 4/13$ points. We estimate to have around 18,000 patients discharged during the 20-month study period, 30% of which (5,400) will be at higher-risk for a 30-day readmission or death. This should be enough to reach the targeted sample size within the study time frame.

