6.1 Outcome definition

6.1.1 Primary outcome

The primary outcome is the number of patients who have an unplanned readmission or die within 30 days after discharge.

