6.2 Outcome derivation

Table 8: Derivation of primary and secondary outcomes.

Outcome	eCRF sheet	Variable	Variable type	Derivation	Outcome type
Primary: Unplanned readmission or death within 30 days after discharge	Baseline Characteristics	discharged_alive	Binary: No, Yes	discharged_alive==No or	Binary
	Follow-up calls	reas_pat_notre_d3, reas_pat_notre_d14	Categorical: Death, No answer, Other	reas_pat_notre_d3==Death or	
	Outcomes 30 days	death_d30	Binary: No, Yes	reas_pat_notre_d14==Death or	
Deaths within 30 days after discharge	Baseline Characteristics	unplanned	Integer: 0-6	death_d30==Yes or	Binary
		discharged_alive	Binary: No, Yes	unplanned>=1	
		reas_pat_notre_d3, reas_pat_notre_d14	Categorical: Death, No answer, Other	discharged_alive==No or	
Outcomes 30 days	Follow-up calls	death_d30	Binary: No, Yes	reas_pat_notre_d3==Death or	Binary
		reas_pat_notre_d14	Categorical: Death, No answer, Other	reas_pat_notre_d14==Death or	

Outcome	eCRF sheet	Variable	Variable type	Derivation	Outcome type
Unplanned readmission within 30 days after discharge	Outcomes 30 days	unplanned	Integer: 0-6	unplanned>=1	Binary
Time to first unplanned readmission or death	Baseline Characteristics	disch_date_index, baseline_death	Date: dmy	Time: min(30, min[baseline_death, date_death_d3, date_death_d14, date_death_d30 unplanned_in_1, lcontact_date] – disch_date_index)	Time-to-event
	Follow-up calls	date_death_d3, date_death_d14	Date: dmy		
	Outcomes 30 days	date_death_d30, unplanned_in_1	Date: dmy		
	End of Study	lcontact_date	Date: dmy	Failure: Primary==Yes	
Main cause of readmission or death	Follow-up calls	cause_death_d3, cause_death_d14	Free text	Tabulated free text fields will be manually categorized	Categorical
	Outcomes 30 days	dx_read30, cause_death_d30	Free text		
Number of unplanned hospital readmissions	Outcomes 30 days	unplanned	Integer: 0-6	-	Count
Number of planned hospital readmissions	Outcomes 30 days	planned_readmission	Integer: 0-8	-	Count
Total number of unplanned days of hospitalizations	Outcomes 30 days	unplanned_x_in, unplanned_x_out	Date: dmy	unplanned_x_out – unplanned_x_in	Count
Total number of planned days of hospitalizations	Outcomes 30 days	tot_rehosp_days_planned	Continuous: days	-	Count
Number of emergency room visits	Outcomes 30 days	nb_edvisits	Integer	-	Count
Number primary care provider visits	Outcomes 30 days	nb_pcpvisits	Integer	-	Count

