6.3.1.2 Analysis of secondary outcomes

The number of patients that die will be compared between treatment groups using a Mantel-Haenszel risk difference with a two-sided 95% CI⁴ and a Cochran-Mantel-Haenszel test, both stratified for the stratification factors used in randomization.

The risk of 30 day unplanned readmissions in each group will be estimated using the cumulative incidence function with death as competing event calculated from flexible parametric survival models (e.g. using `stpm2` followed by `stpm2_standsurv` in Stata)^{5,6}. Groups will be compared using the cumulative incidence difference with 95% CI and a z-test, based on delta method standard errors and a normal approximation. We will also report the cumulative incidence of the competing event (death without readmission) for each group and the risk difference between groups.

Time to unplanned readmission or death will be graphically depicted by Kaplan-Meier curves for each treatment group. Groups will be compared using a log-rank test stratified for the stratification factors used in randomization. As an effect measure, we will use the restricted mean survival time truncated at 30 days calculated using flexible parametric survival models with the group and factors used at randomization as covariates⁷. The restricted mean survival time for each group and the difference between groups will be reported with 95% CI and a p-value.

The main cause of readmission or death will mainly be analyzed with descriptive statistics. The number and proportion of patients in each category will be shown for both groups.

Count outcomes (number of hospital readmissions, number of days of hospitalization, number of emergency room visits, number of primary care provider visits) will be presented with number of patients, person-time and incidence rate with 95% CI. Groups will be compared using a negative binomial regression with the group and the stratification factors as covariates and the observation time as offset. An incidence rate ratio with 95% CI and p-value will be reported. In case of an excess of zeros and overdispersion that cannot be modeled by the negative binomial distribution we will consider zero-inflated negative binomial regression (e.g. using function `zeroinfl` from R package `pscl`).

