6.3.3 Sensitivity analyses

The following sensitivity analysis will be included for all outcomes:

- 1) Without early readmissions. The primary endpoint will be re-analyzed excluding the patients with unplanned readmissions up to the day after index discharge (i.e. unplanned_1_in - disch_date_index <=1)
- 2) No stratification: All outcomes will be analyzed in crude analyses not adjusting for stratification factors. Binary outcomes will be compared by chis-squared test, continuous outcomes by Student's t-test or the Wilcoxon-Mann-Whitney test, count outcomes using an exact Poisson-test and time-to-event outcomes by a log-rank test. Effects will be presented as non-stratified risk difference, mean difference or Mann-Whitney statistic (i.e. the probability that a random patient from the intervention group will have a higher value than a random patient from the control group), incidence rate ratio, and restricted mean survival time difference, respectively, with 95% CI.
- 3) Primary endpoint based on survival methods. The risk of readmission or death at 30 days for both groups and the risk difference between groups will be calculated with 95% CI and p-values from a z-test using a) a flexible parametric survival model for time to unplanned readmission or death with the group and stratification factors as covariates and b) from the Kaplan-Meier-estimator for time to unplanned readmission or death not using the stratification. CIs for the risk differences and the z-test will be calculated using delta method standard errors and a normal approximation.
- 4) Non-parametric unplanned readmissions: The risk of unplanned readmission at 30 days in the presence of the competing risk of death will be calculated for each group using the non-parametric cumulative incidence function estimator with 95% CI according to Choudhury et al⁸. Stratification will be ignored.

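### Table 8 sets no lower bound on event time, so same-day events and deaths before discharge count as failures but have no time that the log-time models can use

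*SAP*

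**What the plan says.** Section 6.1.1 defines the outcome by events after leaving hospital: "The primary outcome is the number of patients who have an unplanned readmission or die within 30 days after discharge". The derivation in Table 8 (6.2) is wider. Its first condition is "discharged_alive==No or", followed by death recorded at either follow-up call or at day 30, or at least one unplanned readmission. No minimum interval after discharge applies.

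For the time-to-event outcome, failure is the primary outcome itself, and time is "Time: min(30, min[baseline_death, date_death_d3, date_death_d14, date_death_d30 unplanned_in_1, lcontact_date] – disch_date_index"). All components are calendar dates. The offset for the count outcomes uses the same dates, except that the date of the first unplanned readmission is left out.

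These times feed the cumulative incidence of readmission (6.3.1.2, for which Table 8 gives no separate time), the "restricted mean survival time truncated at 30 days calculated using flexible parametric survival models" (6.3.1.2) and sensitivity analysis 3a, the survival-based version of the primary endpoint (6.3.3). Section 6.4.1 adds log time to the imputation model for survival outcomes.

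Section 6.4 assigns one day, both as censoring time and as offset, to drop-outs. It gives no such rule for patients with an event.

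**The concern.** Flexible parametric models work on the log of time, and a count model with observation time as offset works on its log. Neither can take a value of zero or below.

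The plan itself expects such cases. Sensitivity analysis 1 is built on "excluding the patients with unplanned readmissions up to the day after index discharge", written as a date difference of at most 1, which includes 0. Section 4.3 lists patients not discharged alive as a major deviation, Table 8 holds a separate date for their death, and the full analysis set (4.4.1) keeps everyone randomised.

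At stake is whether the survival analyses describe the same events as the primary analysis. Sensitivity analysis 3a is there to check the primary result. If it runs on fewer events because some have no usable time, part of any disagreement is an artefact. Sensitivity analysis 1 is blurred too: in the log-time models, part of the group it means to remove would already be gone.

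**Working it through.** **Step 1: apply the Table 8 formulas.** Day 0 is the date in `disch_date_index` unless stated.

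| Case | Event time | Count offset |
|---|---|---|
| Death in hospital, discharge date = date of death | 0 | 0 |
| Death in hospital, discharge date entered 2 days after death | -2 | -2 |
| Death in hospital, discharge date missing | missing | missing |
| Death on the discharge day, after leaving | 0 | 0 |
| Same-day unplanned readmission, last contact day 30 | 0 | 30 |
| Same-day unplanned readmission, death day 5 | 0 | 5 |
| Drop-out, no event (rule in 6.4) | 1 | 1 |

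Every row but the last is a primary event under Table 8, and none of these events has a positive time. The offset fails only for deaths before or on the discharge day. Same-day readmissions keep a positive offset because the readmission date is not in that formula.

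**Step 2: the plan's own figures, as a base.** Inputs from 2.3: 27% in controls and a 25% relative reduction, so 0.27 × 0.75 = 0.2025. Inputs from 4.2: two-sided 5%. The plan states: "Allowing for 10% loss to follow-up, we determine that we will need 1,380 patients for the study to have 80% power". With the mean proportion 0.23625:

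n = [1.960 × √(2 × 0.23625 × 0.76375) + 0.8416 × √(0.27 × 0.73 + 0.2025 × 0.7975)]² / 0.0675² = 620.5, so 621 per arm.

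621 / 0.9 = 690 per arm, 1,380 in total. The stated figure is reproduced. Expected events among 621 per arm: 621 × 0.27 ≈ 168 and 621 × 0.2025 ≈ 126.

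**Step 3: what losing events would do.** The SAP gives no number of such events, so the losses below are assumed. Lost patients leave both numerator and denominator. Simple proportions stand in for the modelled risks of sensitivity analysis 3a.

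| Assumed loss | Lost, control / intervention | Risk, control / intervention | Difference (points) |
|---|---|---|---|
| none | 0 / 0 | 168/621 = 27.1% / 126/621 = 20.3% | -6.8 |
| 1% of events | 2 / 1 | 166/619 = 26.8% / 125/620 = 20.2% | -6.7 |
| 5% of events | 8 / 6 | 160/613 = 26.1% / 120/615 = 19.5% | -6.6 |
| 10% of events | 17 / 13 | 151/604 = 25.0% / 113/608 = 18.6% | -6.4 |
| 5 in control only | 5 / 0 | 163/616 = 26.5% / 126/621 = 20.3% | -6.2 |
| 5 in intervention only | 0 / 5 | 168/621 = 27.1% / 121/616 = 19.6% | -7.4 |

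**Step 4: does the value of the floor matter?** Moving k zero-time events to 0.5 or 1 day changes an arm's restricted mean by k × 0.5/621 or k × 1/621. For k = 1 to 10 that is 0.001 to 0.016 days. Dropping k zero-time patients instead raises an arm's mean by up to 30 × k/621 days, ignoring censoring; for k = 5 that is at most 0.24 days. In a simulated negative binomial fit with 3 zero exposures among 400 patients, the fit failed with zeros and ran with either floor (group coefficient -0.2254 with 0.5 day, -0.2249 with 1 day). The value matters little; having a rule matters.

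**The case against.** The strongest reply is that the main result does not depend on any of this. The Mantel-Haenszel risk difference and the Cochran-Mantel-Haenszel test in 6.3.1.1 use a binary outcome and no time variable. A reader might infer that the primary analysis loses events; it does not. Deaths before discharge are also major deviations, so the per-protocol set excludes them (same-day readmissions stay in it).

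Second, a reader might infer that the count models lose same-day readmissions as well. The offset formula rules that out, as Step 1 shows.

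Third, a time of exactly zero for deaths in hospital is one possibility only. It requires `disch_date_index` to hold the date of death, and the SAP does not say that. The alternatives, negative or missing, are no more usable, so the gap stands.

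Fourth, numbers are likely to be small: eligibility requires an expected live discharge, and nothing in the SAP supports a particular rate of deaths before discharge or same-day readmissions. Any percentage of events lost is an assumption.

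Fifth, the loss need not pass unnoticed. A model may fail outright, as the simulated fit did, and 3.2 requires date-consistency checks before lock. That stands, but it would leave the repair to be chosen after the data are seen.

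Sixth, sensitivity analysis 3a differs from the primary analysis by design anyway, because drop-outs are non-events in one and censored at one day in the other. That is true, and an unplanned second difference would be hard to separate from it.

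**Conclusion.** The gap is real and confined to secondary and sensitivity analyses: cumulative incidence of readmission, restricted mean survival time, sensitivity analysis 3a, the log-time term in the imputation and, for deaths before or on the discharge day only, the count models. Followed as written, Table 8 gives these analyses a different event set from the primary analysis, with the earliest events missing. The one-day rule in 6.4 does not close the gap, since it covers drop-outs only: patients assumed event-free keep a usable time while patients with an observed day-0 event do not.

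The size cannot be fixed from the SAP. Under the assumed losses in Step 3 the effect is at most 0.4 points when balanced (-6.8 to -6.4) and about 0.6 points either way for 5 events lost in one arm. It is likely small unless the loss is unbalanced. The documents do not support a stronger claim, such as a definite number of patients lost per arm or a bias in the primary result.

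A separate point does touch the primary outcome: 6.1.1 speaks of events after discharge, while Table 8 also counts patients who never left hospital alive. Which is meant has to be stated.

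**What to change.** In Table 8:

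- Set a positive floor for event times and for the offset where it is limited by death. Half a day is one choice; state it alongside the one-day convention for drop-outs in 6.4, so that the two rules are visibly deliberate.
- State how `disch_date_index` is set for patients who die before discharge, and what time they are assigned.
- Require the number of failures in the survival analyses to equal the number of primary events in the same analysis set, with any difference explained. For the competing-risk analysis, readmissions plus deaths without readmission should add up to that number.

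Separately, reconcile 6.1.1 with Table 8 on deaths before discharge. If such deaths are not meant to count, the floor is still needed for same-day events, and the handling of these patients in the full analysis set must then be stated.

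The cost is a few lines in 6.1.1, 6.2 and 6.4 before database lock, with no new data and no change to the sample size or the primary test.

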5.6 Procedural characteristics

Procedural characteristic include the components of the transitional care intervention and are collected for the transition care group only. The pre-discharge component of the intervention is documented at baseline (visit 1) on eCRF “Pre-discharge component”, the follow-up phone calls (visit 2 and visit 3) on eCRFs “Follow-up call 1 (Day 3)” and “Follow-up call 2 (Day 14)”. Evaluations of the procedural characteristics will be based on the FAS. They will be presented in a descriptive summary table—continuous variables as mean and standard deviation or median and quartiles and categorical variables as absolute and relative frequencies.

Table 6: Procedural characteristics: pre-discharge components.

Description	Variable	Type
Basic information about her/his main diseases has been performed?	pat_info	Binary: No, Yes
Which information about those comorbidities have been given to the patient?		
Heart failure	inf_shee_giv_1	Binary: Unchecked, Checked
Coronary disease	inf_shee_giv_2	Binary: Unchecked, Checked
Peripheral artery disease	inf_shee_giv_3	Binary: Unchecked, Checked
Atrial fibrillation	inf_shee_giv_4	Binary: Unchecked, Checked
Chronic obstructive lung disease	inf_shee_giv_5	Binary: Unchecked, Checked
Stroke	inf_shee_giv_6	Binary: Unchecked, Checked
Gastrointestinal bleeding	inf_shee_giv_7	Binary: Unchecked, Checked
Chronic renal failure	inf_shee_giv_8	Binary: Unchecked, Checked
Liver cirrhosis	inf_shee_giv_9	Binary: Unchecked, Checked
Thromboembolism	inf_shee_giv_12	Binary: Unchecked, Checked
Diabetes	inf_shee_giv_13	Binary: Unchecked, Checked
Other*	inf_shee_giv_88	Binary: Unchecked, Checked
No listed comorbidity	inf_shee_giv_0	Binary: Unchecked, Checked
Medication reconciliation has been performed and explanation about medication list?	med_reco	Binary: No, Yes
Have you noticed any medication discrepancy that needed to be transmitted to the medical team?	med_reco_disc	Binary: No, Yes
Patient education about general health recommendation has been performed?	pat_educ	Binary: No, Yes
Dependence Level: score of the Katz Index	katz_ind	Integer: 0-6
Post discharge follow-up visit to the treating physician has been planned?*	folup_plan	Binary: No, Yes
Discharge summary sent to the treating physician	dis_sumpcp	Binary: No, Yes
Barriers to a safe discharge, including patient's ability to carry out the discharge plan has been assessed	finalcheck	Binary: No, Yes

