Offset for count variables	Baseline Characteristics	disch_date_index, baseline_death	Date: dmy	min(30, min[baseline_death, date_death_d3, date_death_d14, date_death_d30 lcontact_date] – disch_date_index)	Continuous
	Follow-up calls	date_death_d3, date_death_d14	Date: dmy		
	Outcomes 30 days	date_death_d30	Date: dmy		
	End of Study	lcontact_date	Date: dmy		
Patient's perspective (satisfaction) on quality of transition of care between hospital and home (CTM-3)	Outcomes 30 days	ctm1, ctm2, ctm3	Binary: No, Yes	ctm1==Yes & ctm2==Yes & ctm3==Yes	Binary
Costs of readmission	Costs at Outcomes 30 days	costs_30d	Continuous: CHF	-	Continuous

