6.7 Quality control

A second statistician will reproduce the analysis of the primary outcome (for both the FAS and the PPS) based on the exported data. The risk difference and the 95% confidence interval should not differ by more than 0.01, the p-value by 0.001. Otherwise, the reason for the difference will be determined and a consensus must be reached.

7 Changes from the protocol

The SAP is consistent with principle features of the statistical methods described in the protocol. The following deviations were made:

Table 10: Changes from protocol

Header	Change	Reason
Blinded analysis	Blinded analysis not implemented	The allocation can immediately be seen from the eCRFs because only patients in the intervention group have follow up phone calls. It would therefore need an extra statistician that carefully prepares the data so that it is not possible to see the allocation. Given the open-label nature of the study and the straightforward analysis this additional effort seems not to be justified.
Secondary outcome "Medication adherence: 4-item Morisky Medication Adherence Scale (MMAS-4)".	Removed	High license fees would incur
Secondary endpoint "Number of planned hospital readmissions" and "Total number of planned days of hospitalizations"	Added	Information about the planned readmissions is of interest but was not considered in the protocol.
Test for the analysis of primary and binary secondary outcome	Stratified Cochran-Mantel-Haenszel test instead of simple chi-squared test	Stratification factor should be considered in the analysis
Subgroup HOSPITAL score	Categories 4 or 5 vs ≥ 6 instead of 5 or 6 vs ≥ 7	Categories correspond to stratification of the randomization
Subgroup clinical site	Added	Used as stratification factor in randomization
Subgroups cancer, living place, living status and health insurance	Added	Of interest, not mentioned in protocol

References

¹ Clinical trial protocol: Transition care intervention targeted to high-risk patients to reduce readmission (TARGET-READ): A randomized controlled trial, Version 1.1, 13.02.2018

² SOP Data preparation and programming, CS_STA_SOP_05, version 02, 15.08.2015

³ SOP Statistical data validation, CS_STA_SOP_02, version 02, 15.08.2015

⁴ Klingenberg, B. 2014. A new and improved confidence interval for the Mantel–Haenszel risk difference. *Statistics in medicine*, 33(17): 2968.

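### Table 8 lets the last-contact date override a recorded death, so event times and offsets of patients who died can be shortened, by different amounts in the two arms

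*SAP*

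**What the plan says.** SAP section 6.2, Table 8, defines the time to first unplanned readmission or death as the smaller of 30 days and a minimum over dates, less the index discharge date. The minimum covers the death dates, the first unplanned readmission and the last contact, and ends "lcontact_date] – disch_date_index". The event indicator is given separately as "Failure: Primary==Yes". Nothing restricts `lcontact_date` to patients without an event.

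The offset for the count outcomes is built in the same way, without the readmission date: "min(30, min[baseline_death, date_death_d3, date_death_d14, date_death_d30 lcontact_date] – disch_date_index".

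The two arms have different contact schedules. Section 5.6 says that the intervention components, including the calls, "are collected for the transition care group only". Section 7, Table 10, adds that "only patients in the intervention group have follow up phone calls". Section 2.7 places those calls at days 3 and 14, and section 6.4 says that outcomes are assessed once only.

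`lcontact_date` is listed as an End of Study field. The SAP does not say what it holds for a patient who has died.

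**The concern.** A last-contact date is a censoring date and belongs only to patients without an event. Inside the minimum for everyone, with failure taken from the primary outcome, it makes a patient with an earlier last contact fail on the contact date, although the true death date stands in the same formula. That patient's observation time for the count models is cut as well.

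If the field holds the last contact with the living patient, the size of the shift depends on the arm. An intervention patient may have been reached at day 3 or day 14. A control patient has no scheduled contact between discharge and the day-30 assessment, so the death could be dated to about day 0. At stake are the restricted mean survival time (the effect measure for a named secondary outcome, section 6.3.1.2), the shape of the Kaplan-Meier curves, the survival models that use this time (section 6.3.3, item 3), and the offsets of patients who died.

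**Working it through.** **Inputs from the SAP.** Control risk 27% and relative reduction 25%, so 20.25% under intervention (section 2.3); calls at days 3 and 14 (section 2.7). The two risks reproduce the planned size: two-sided 5% and 80% power give 621 per arm, and 621/0.9 = 690, so 1,380 in total. No stated figure is disputed.

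**Assumptions, not in the SAP.** 3-5% of patients die without prior readmission, equally in both arms; readmission about 24%; last contact recorded before death in 10-50% of deaths; last contact at day 0 in controls and at the latest of days 0, 3 and 14 before death in the intervention arm; deaths spread evenly over 30 days; no true effect. The hand calculation uses a 27% composite risk.

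**Planned effect in days.** With constant hazard h = -ln(1 - p)/30, the restricted mean to day 30 is p/h.
- Control: h = 0.01049, 0.27/0.01049 = 25.74 days.
- Intervention: h = 0.00754, 0.2025/0.00754 = 26.85 days.
- Difference: about +1.1 days.

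**Mean backward shift per affected death.**
- Control: 15 days.
- Intervention: (3×1.5 + 11×5.5 + 16×8)/30 = 6.43 days.
- Difference: 8.57 days.

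**Share of patients affected, q.** Lowest 0.03×0.10 = 0.003; highest 0.05×0.50 = 0.025. The share of control events on day 0 is 0.003/0.27 = 1% to 0.025/0.27 = 9%. In the intervention arm only deaths before day 3 go to day 0, one tenth of those moved, so at most about 1%.

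**Case A: day-0 failures kept.** The spurious difference (intervention minus control) is q×8.57.
- q = 0.003: +0.026 days.
- q = 0.025: +0.21 days.

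Simulation with 3 million patients per arm, keeping day-0 events at half a day, gives +0.02 to +0.20. The number of events by day 30 is unchanged.

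**Case B: day-0 failures dropped.** The control mean becomes (25.74 - 15q)/(1 - q). In the intervention arm 0.1q is dropped (mean time 1.5 days), and 0.9q stays with a mean shift of (11×5.5 + 16×8)/27 = 6.98 days.
- q = 0.003: control 25.772, intervention 25.728, difference -0.04 days.
- q = 0.025: control 26.015, intervention 25.643, difference -0.37 days.

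The simulated range is -0.04 to -0.38. Here the 30-day risk moves too. At q = 0.025 it is (0.27 - 0.025)/0.975 = 25.1% in controls and (0.27 - 0.0025)/0.9975 = 26.8% in the intervention arm, a spurious +1.7 percentage points.

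**Tests, if every such death is shifted and all events are kept** (690 per arm, no true effect). This goes beyond the 10-50% range. The restricted mean test rejects in 8.5% of trials at 3% deaths and 13.8% at 5%, against a nominal 5%. The log-rank test stays at 4.8-5.7%. With each death at its own date, the restricted mean test returns to 4.6-5.8%.

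**The case against.** The strongest reply is that the premise is not in the document. How `lcontact_date` is filled for a deceased patient would be set in the eCRF or data dictionary. Table 7 lists next of kin, treating physician, hospital and death certificate as sources on a death, so a contact on or after the death is a plausible entry, and the formula is then harmless. Section 3.2 also plans checks on date sequence before database lock, which might catch a known death with an event time of zero. This stands as far as it goes: the error is conditional. But the checks do not change the formula, and a last contact before a death is a valid sequence that need not be queried. The day-1 rule in section 6.4 covers drop-outs, not deaths.

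A reader might infer more than the SAP supports:
- **That the primary result is biased.** The primary outcome is binary and its Mantel-Haenszel and Cochran-Mantel-Haenszel analyses (section 6.3.1.1) use no dates.
- **That the error favours one particular arm.** The sign reverses with the handling of day-0 failures, on which the SAP gives no rule.
- **That the log-rank test and the 30-day risks are distorted in any case.** They change materially only if day-0 failures are dropped.
- **That controls have no contact after discharge.** They have the day-30 outcome assessment. Patients alive at that assessment, including those already readmitted, are contacted after their event, so most events keep their date.

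**Conclusion.** The point holds as a conditional defect in a derivation. The stated rule misdates any death that follows the recorded last contact and shortens that patient's offset, and the calls in one arm only would make the shift unequal. Under the assumptions listed, the spurious restricted mean difference is about -0.04 to -0.38 days if day-0 failures are dropped and about +0.02 to +0.20 days if they are kept, against a planned effect of about +1.1 days. At worst that is roughly a third of the planned effect. The mortality, the share of deaths affected and the contact days are assumptions; if the field always holds the death date or later, the error is zero. The effect on the count rate ratios was not quantified; it arises only through patients who died. The change should be made, but it concerns secondary and sensitivity analyses only.

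**What to change.** Rewrite the two derivations in Table 8 before database lock:
- **Time to event.** If Primary==Yes, take the earliest recorded event date minus the discharge date. Otherwise use `lcontact_date`, capped at 30 days, only to censor, and keep the drop-out rule of section 6.4.
- **Offset.** Use the death date if the patient died, otherwise the censoring date, with the same cap.
- **Definition.** State what `lcontact_date` holds for a deceased patient.
- **Day 0.** State how events on the day of discharge are kept in the analysis, so that the result does not depend on a software default.

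The cost is a few lines of text and code. No new data are needed, the sample size is unaffected, and the change does no harm if the field turns out to hold the death date.

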2.8 Blinding

Most of the study personal including PI, study nurses, statistician and data manager will not be blinded. However, the study nurses collecting the outcomes or working on data cleaning will be blinded to the group allocation.

3 Data management

The CRFs in this trial are implemented electronically using a dedicated electronic data capturing (EDC) system (REDCap, <https://www.project-redcap.org/>). The EDC system is activated for the trial only after successfully passing a formal test procedure. All data entered in the CRFs are stored on a Linux server in a dedicated mySQL database. Responsibility for hosting the EDC system and the database lies with CTU Bern.

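### Causes of death and readmission are hand-coded from free text with no masking stated, and the cause row lists no source for deaths before discharge

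*SAP*

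**What the plan says.** Section 6.1.2 lists the main cause of readmission or death as a secondary outcome. Section 6.3.1.2 plans a mainly descriptive analysis, with counts and percentages per category by arm.

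Table 8 (section 6.2) builds the outcome from four free-text fields. Two come from the follow-up call forms, "cause_death_d3, cause_death_d14", and two from the 30-day outcome form, "dx_read30, cause_death_d30". The derivation is one line: "Tabulated free text fields will be manually categorized".

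On blinding, section 2.8 states: "Most of the study personal including PI, study nurses, statistician and data manager will not be blinded". It then makes an exception for the nurses who collect outcomes or clean data, who are blinded. Table 10 (section 7) withdraws the blinded analysis. It notes that the forms show the arm, because follow-up calls take place only in the intervention group, and concludes: "Given the open-label nature of the study and the straightforward analysis this additional effort seems not to be justified". Section 5.6 confirms that the intervention components, including the calls, "are collected for the transition care group only".

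For the primary outcome and for 30-day death, the first condition in Table 8 is "discharged_alive==No or", taken from the Baseline Characteristics form.

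**The concern.** Sorting free text into causes is a matter of judgement. Table 10 drops blinding on the ground that the analysis is simple. That can be argued for a Mantel-Haenszel comparison of counts, but not for this step. A coder who sees the arm can, without meaning to, place ambiguous texts differently in the two groups, and so create or hide a difference in causes. Section 6.5 plans no safety evaluation, which leaves this table as the only planned between-group comparison of what patients died of or were readmitted for.

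The second part is a mismatch within Table 8. Deaths before discharge count as primary events, but the cause row draws on no field from the form on which they are recorded. A cause table that adds up to fewer patients than the primary outcome, with no explanation, is harder to read.

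**Working it through.** **1. The design figure.** Inputs from sections 2.3 and 4.2: 27% in usual care, a 25% relative reduction, two-sided 5%, 80% power, 10% loss. Intervention rate = 0.27 × 0.75 = 0.2025; mean rate = 0.23625.

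n per arm = [1.960 × √(2 × 0.23625 × 0.76375) + 0.842 × √(0.27 × 0.73 + 0.2025 × 0.7975)]² / (0.27 − 0.2025)², which rounds up to 621. Then 621 / 0.9 = 690 per arm, 1,380 in total. The SAP's figure is reproduced, and this point does not dispute it.

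**2. The size of the coding task.** Expected primary events = 690 × 0.27 + 690 × 0.2025 = 186.3 + 139.7 ≈ 326. With 10% lost, 326 × 0.9 ≈ 293. This is roughly how many patients have a cause to be coded. It is not a count of biased codes.

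**3. Can the coder see the arm?**
- The coder is not named. Of the roles in section 2.8, the principal investigator, the statistician and the data manager are unblinded; the nurses who collect outcomes or clean data are blinded.
- Two of the four source fields come from call forms completed in one arm only. An entry listed under either field name comes from an intervention patient.
- The two fields from the 30-day form carry no arm in their names, but Table 10 accepts that the data as a whole show the allocation.

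The SAP therefore allows coding with the arm visible and does not require masking.

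**4. Table 8, row against row.**

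| Form | Used for primary outcome or 30-day death | Used for time to event | Used for cause |
|---|---|---|---|
| Baseline Characteristics | discharged_alive | "disch_date_index, baseline_death" (dates) | none |
| Follow-up calls | reason not reached = death | dates of death | "cause_death_d3, cause_death_d14" |
| Outcomes 30 days | death_d30, unplanned | date of death, date of readmission | "dx_read30, cause_death_d30" |

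Only the cause row leaves out Baseline Characteristics. Such deaths are foreseen: section 4.3 lists patients not discharged alive as a major deviation, and section 4.4.1 keeps every randomised patient in the full analysis set. Their cause enters the table only if someone writes it in cause_death_d30, and the SAP does not say whether that form is completed for them.

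**5. The size of the shortfall.** The SAP gives no rate of death between randomisation and discharge, so the rate q is an assumption. Expected deaths = 1,380 × q; share = expected deaths / 326; chance of at least one = 1 − (1 − q)^1380.

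| Assumed q | Expected deaths | Share of primary events | Chance of at least one |
|---|---|---|---|
| 0.1% | 1.4 | 0.4% | 75% |
| 0.5% | 6.9 | 2.1% | 99.9% |
| 1% | 13.8 | 4.2% | nearly 100% |

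These are upper limits for the shortfall at each rate, because any cause entered on the 30-day form reduces it.

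**The case against.** The SAP does not say who codes. Blinded nurses exist, the protocol or the cited procedures may assign the task to them, and a tabulated list of texts could be coded without patient number or arm. A reader might infer that all of the roughly 326 events will be coded with the arm open. The document does not support that: open coding is permitted, not stated, and only deaths learned of at an intervention call sit in fields that reveal the arm by name.

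A reader might also infer that the cause table is bound to disagree with the primary events and so cannot be interpreted. That too goes beyond the text. It needs at least one death before discharge with no cause on the 30-day form, and a gap of a few per cent would not make the table unreadable. The gap could also be traced: discharge status is tabulated by arm (Table 4), patients not discharged alive are summarised by arm (section 4.3), and section 6.4 reports the number of non-missing observations for each outcome.

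Finally, the outcome is secondary and mainly descriptive, with no test specified.

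All of this limits the size of the point. It does not answer it. Masking is nowhere required for the one outcome that depends on reading text, the stated reason for dropping blinding does not fit that step, and the cause row still differs from its neighbours.

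**Conclusion.** The point holds as a cheap improvement to a secondary, mainly descriptive outcome. Causes may be coded with the arm visible, and this could bias the comparison of causes. The size of that bias cannot be calculated from the SAP. The primary test is not affected.

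The cause table may also fall short of the primary events by the number of deaths before discharge whose cause is not entered in cause_death_d30. That number is not given. On assumed rates of 0.1% to 1% it is at most about 1 to 14 patients, or 0.4% to 4.2% of the expected primary events, and it is zero if no such death occurs. The conclusion assumes that Table 8 is followed as written and that no unseen document already prescribes masked coding.

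**What to change.** Add the following to section 6.2 before any cause is coded:

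- Pool all cause texts into one extract with a neutral row key, leaving out allocation, visit and variable name.
- Have the already-blinded outcome nurses code the texts to a list fixed beforehand. The main_dx_at categories in Table 5 could serve, with a trauma/accident category added: that list has none, while the call forms record traumatic deaths (Table 7).
- Merge allocation only after coding is finished.
- Show deaths before discharge for which no cause was recorded in a separate row, 'died before discharge / cause not recorded'. The SAP lists no cause field on Baseline Characteristics, so this row avoids having to collect one.
- Reconcile the table total, counted in patients, with the number of primary events.

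The cost is SAP wording, one data-preparation step and a few hours of blinded staff who are already in place. Masking cannot remove clues inside the text itself, but it removes those carried by the data structure.
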